4.2. Inclusion Criteria

Subjects must meet all the following inclusion criteria to be eligible for study participation:

1. Males and non-pregnant, non-lactating females between 18 - 75 years of age inclusive, at the time of the screening visit.
2. Previous history or presence of 2 out of 4 components of metabolic syndrome (obesity, dyslipidemia, elevated blood pressure, elevated fasting glucose) or type 2 diabetes.
3. **Initial Screening Visit:** After a signed informed consent and confirmation of clinical risk profile associated with NASH, a screening lab panel and elastography will be measured for all subjects during an initial screening period:

- a. FibroScan® median liver stiffness > █

- b. CAP █

Note: All subjects must complete a FibroScan® examination during the screening period. However, the median liver stiffness and CAP inclusion criterion do not apply to subjects with an eligible historical liver biopsy performed \leq 180 days prior to randomization which confirmed fibrosis 1-3 and a NAS \geq 4.

If a historical value for FibroScan® is available in the past 3 months prior to the Screening Visit, then the FibroScan® does not need to be repeated.

- c. AST $>$ 17 for females and $>$ 20 for males;

Note: The AST inclusion criterion does not apply to subjects with an eligible historical liver biopsy performed \leq 180 days prior to randomization which confirmed fibrosis 2-3 and a NAS \geq 4.

- d. Estimated glomerular filtration rate (eGFR) \geq 60 mL/min, as calculated by the CKD-EPI equation;
- e. HbA1c \leq 9.5% (or serum fructosamine \leq 381 μ mol if HbA1c is unavailable);
- f. INR \leq 1.3, unless due to therapeutic anticoagulation;
- g. Direct bilirubin \leq ULN;
- h. Total bilirubin \leq upper limit of normal (ULN), unless due to an alternate etiology such as Gilbert's syndrome or hemolytic anemia;
- i. Creatinine kinase $<$ 3 x ULN;
- j. Platelet count \geq 140,000/ μ L;
- k. Triglyceride level \leq 500 mg/dL;
- l. ALT $<$ 5 x ULN;

- m. AST < 5 x ULN;
- n. ALP < 2 x ULN.

Note: Subjects meeting all of the above components will move into the next screening phase.

4. Documented historical stability (4 weeks to 6 months prior to screening) of ALT and AST levels showing no worsening at screening based on the following:
 - a. If the historical and screening ALT and AST values are both $\leq 1.5 \times$ the upper limit of normal (ULN), there is no limit to the difference between the values.

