4.3. Exclusion Criteria

Subjects meeting any of the following criteria are not eligible for study participation:

1. Weight loss > 5% in the 3 months prior to screening until randomization or from the time of the diagnostic liver biopsy until randomization, whichever is longer.
2. Presence of cirrhosis on liver biopsy (stage 4 fibrosis).
3. Type 1 diabetes.
4. Uncontrolled Type 2 diabetes defined as:
 - a. Insulin dose adjustment >35% within 30 days prior to screening through randomization,
 - b. Symptoms of the following within 3 months prior to screening: acutely decompensated blood glucose control (e.g., thirst, polyuria, weight loss), or a history of diabetic ketoacidosis, or a history of hyperglycemic hyperosmolar state
5. Hypoglycemia unawareness, hospitalization due to hypoglycemia, or history of severe hypoglycemia (hypoglycemia requiring outside assistance to regain normal neurologic status) within 3 months prior to screening.
6. Subjects with osteoporosis, defined as a T-score of -2.5 or lower at screening.
7. Poorly controlled hypertension (systolic blood pressure > 160 mm Hg, or diastolic blood pressure > 100 mm Hg).
8. Any prior history of decompensated liver disease including ascites, hepatic encephalopathy (HE), or variceal bleeding.
9. History of pancreatitis.
Note: Subjects with a history of gallstone pancreatitis and subsequent cholecystectomy may be allowed to participate upon approval by the Medical Monitor.
10. Chronic hepatitis B virus (HBV) infection (hepatitis B surface antigen [HBsAg]) positive or acute hepatitis A infection (hepatitis A IgM antibody positive).
11. Chronic hepatitis C virus (HCV) infection (HCV antibody [Ab] and HCV ribonucleic acid [RNA] positive). Subjects cured of HCV infection < 2 years prior (based on date of RNA polymerase chain reaction [PCR] negative confirmation following conclusion of treatment) to the screening visit are not eligible.
12. Prior (< 2 years prior to screening) or planned (during the study period) bariatric surgery (e.g., gastroplasty, roux-en-Y gastric bypass). Surgery failure or reversal or removal of intragastric balloon > 2 years prior to screening would be acceptable.

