6.25.1. Hepatic Events Adjudication Committee

A key objective of this study is to prevent progression to cirrhosis and associated complications. Clinical events that constitute the clinical outcomes endpoint include:

- 1) Progression to cirrhosis as defined by a liver biopsy showing F4 fibrosis according to the NASH CRN classification, as assessed by the central reader.
- 2) Events of hepatic decompensation including:

- a) Clinically apparent ascites requiring treatment
- b) HE of Grade 2 or above (according to the West Haven criteria defined in [Appendix E](#)) requiring treatment
- c) Portal hypertension-related upper gastrointestinal bleeding identified by endoscopy and requiring hospitalization, including events of bleeding from esophageal varices, gastric varices, and portal hypertensive gastropathy
- 3) Liver transplantation or qualification for liver transplantation, defined as MELD score ≥ 15 (unless due to therapeutic anticoagulation) on at least 2 consecutive occasions at least 4 weeks apart
- 4) All-cause mortality

Each of the clinical events (except histologic progression to cirrhosis, all-cause mortality and liver transplantation) will require confirmation by a Hepatic Events Adjudication Committee. All deaths will be reviewed by this committee to determine if they are liver-related.

If there is clinical evidence that a subject has progressed to cirrhosis (e.g., based on the presence of new esophageal varices, changes in biomarkers [including, but not limited to, low serum albumin, high serum bilirubin, a low platelet count, prolonged INR, or elevated liver stiffness], or development of other clinical signs or symptoms of cirrhosis), the subject should undergo repeat liver biopsy for confirmation of progression to cirrhosis (F4 fibrosis as assessed by the central reader according to the NASH CRN classification) at the discretion of the principal investigator (PI).

Once the clinical event (except histological progression to cirrhosis, all-cause mortality and liver transplantation) is confirmed by the Hepatic Events Adjudication Committee, the subject will discontinue from the study. Subjects who experience histological progression to cirrhosis, all-cause mortality and liver transplantation will be discontinued from the study, but do not require confirmation from the adjudication committee prior to discontinuation.

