Exploratory: fibrosis stage and NAFLD Activity Score (NAS) on liver histology at Week 24 and Week 96	LBAS PPS
Exploratory: event-free survival (EFS)	FAS
Exploratory: adjudicated cardiovascular endpoints at Week 48, Week 96 and end of study	FAS
Exploratory: bone biomarkers change from baseline	Biomarkers Analysis Set
Exploratory: cardiovascular and metabolic risk factors (e.g., incidence of Type 2 Diabetes, body mass index (BMI), and blood pressure)	Safety Set
Exploratory: non-invasive measures of fibrosis associated with histological regression and/or progression of fibrosis and clinical complications of cirrhosis	LBAS
Exploratory: markers of liver injury and function	FAS LBAS
Exploratory: MRI-PDFF based quantitation of hepatic fat	MRI-PDFF Analysis Set
Exploratory: Plasma concentrations of EFX	PK Analysis Set
Exploratory: waist-to-hip ratio change from baseline	FAS PPS
Exploratory: health-related quality of life (CLDQ-NASH) change from baseline	FAS PPS
Safety Endpoints	
Concomitant medications	Safety Set
Extent of exposure	Safety set
Adverse events (AEs)	Safety set
Laboratory evaluations, electrocardiogram (ECG) and vital sign assessments	Safety set
Bone Mineral Density	Safety Set

CONFIDENTIAL

Statistical Analysis Plan

Sponsor Name: Akero Therapeutics, Inc.
Sponsor Protocol ID: AK-US-001-0102

Outcome Variable	Analysis Set(s)
Endogenous FGF21	Safety Set
Anti-drug antibody (ADA) and neutralizing antibody (NAb)	Safety set

¹ Apply rules for intercurrent events as for primary efficacy endpoint.

6. Data Handling

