7.6.3.7 Changes in cardiovascular and metabolic risk factors

The analysis of changes in cardiovascular and metabolic risk factors will be performed using the Safety Set. Descriptive summaries and boxplots of BMI and blood pressure will be presented by treatment group and visit.

An MMRM model with baseline covariate will be used to evaluate the changes from baseline in blood pressure between the EFX arms and the placebo arm at scheduled visits, controlling for stratification factors. Least square (LS) means, 95% CIs, and p-values will be presented. The analysis will be performed using the Safety Set.

A CMH test will be used to compare the differences in proportions of subjects with new onset of T2D between the EFX arms and the placebo arm, adjusting for stratification factors. The new onset of T2D is defined as a single HbA1C value of 6.5% or higher when baseline HbA1c <6.5%. The analysis will be performed using the Safety Set.

7.6.3.8 Non-invasive measures of fibrosis can predict histological regression and/or progression of fibrosis and clinical complications of cirrhosis

Correlation models will be fitted to explore the correlation coefficient between non-invasive measures of fibrosis and histological fibrosis (CRN fibrosis stage of liver biopsy) and clinical complications of cirrhosis (MELD score and CP score). Non-invasive measures of fibrosis include serum biomarkers (ELF and Pro-C3) and imaging (liver stiffness by FibroScan). In addition, correlation between the imaging marker for hepatic fat (MRI-PDFF) and histological fibrosis and NASH resolution will also be explored. The analysis will be performed using the LBAS.

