7.6.3.9 Change from baseline in markers of liver injury and function

The analysis of markers of liver injury and function, including ALT, AST, ALP, GGT, bilirubin, INR, albumin, uric acid, platelets, MELD score, and CP score will be performed using the FAS and LBAS. Summaries of actual values and changes from baseline will be presented by treatment group and visit.

CP score will be calculated as below, ranging from 5-15:

	1 point	2 point	3 point
Bilirubin (Total)	<2 mg/dL (<34.2 µmol/L)	2-3 mg/dL (34.2-51.3 µmol/L)	>3 mg/dL (>51.3 µmol/L)
Albumin	>3.5 g/dL (>35 g/L)	2.8-3.5 g/dL (28-35 g/L)	<2.8 g/dL (<28 g/L)
INR	<1.7	1.7-2.2	>2.2

CONFIDENTIAL

Statistical Analysis Plan

Sponsor Name: Akero Therapeutics, Inc.
Sponsor Protocol ID: AK-US-001-0102

Ascites	No ascites	Mild to moderate (diuretic responsive/controlled)	Severe (diuretic refractory/poorly controlled)
Encephalopathy	No Encephalopathy	Grade 1-2	Grade 3-4
Class A = 5-6 points			
Class B = 7-9 points			
Class C = 10-15 points			

An MMRM model with baseline covariate will be used to evaluate the changes and percent changes from baseline in markers of liver injury and function between the EFX arms and the placebo arm at scheduled visits, controlling for stratification factors. LS means, 95% CIs, and p-values will be presented.

Summaries and boxplots will be presented for actual values and changes from baseline in ALT, AST, ALP, GGT, bilirubin, INR, albumin, uric acid, MELD score, and CP score at the collection time points defined in the Schedule of Assessments by treatment group.

7.6.3.10 *MRI-PDFF based quantitation of hepatic fat*

The analysis of MRI-PDFF based quantitation of hepatic fat will be performed using the MRI-PDFF Analysis Set. Summaries of actual values and absolute and percent changes from baseline will be presented by treatment group and visit. A CMH test will be used to compare the differences in proportions of subjects with relative reduction $\geq 30\%$ and $\geq 50\%$ in hepatic fat and with liver fat content $\leq 5\%$ at Week 24 and Week 96 between the EFX arms and the placebo arm, adjusting for stratification factors. The point estimates and 95% CIs for the differences in proportions, and p-values will be calculated. The 95% CI will be constructed using the Miettinen and Nurminen method.

7.6.3.11 *Change from baseline in waist-to-hip ratio*

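### SAP 7.6.3.8 asks whether non-invasive markers predict fibrosis change and complications, but correlates them with fibrosis stage, not change in stage, and with Child-Pugh, which entry criteria hold near its minimum

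*SAP*

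**What the plan says.** The heading of SAP 7.6.3.8 states the aim: "Non-invasive measures of fibrosis can predict histological regression and/or progression of fibrosis and clinical complications of cirrhosis". The method is one sentence, "Correlation models will be fitted to explore the correlation coefficient between non-invasive measures of fibrosis and histological fibrosis", continuing to the clinical scores. The variables set against the markers are "histological fibrosis (CRN fibrosis stage of liver biopsy) and clinical complications of cirrhosis (MELD score and CP score"). The markers are ELF, Pro-C3 and FibroScan stiffness; MRI-PDFF is also correlated with histological fibrosis and NASH resolution. The analysis set is the LBAS. The section states no time point, lag, change variable or treatment adjustment. SAP Table 3 lists the same analysis as "non-invasive measures of fibrosis associated with histological regression and/or progression of fibrosis and clinical complications of cirrhosis".

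Other parts of the plan hold what 7.6.3.8 leaves out. SAP 7.6.3.2 summarises change and shift in fibrosis stage by treatment group, without the markers. Protocol 6.25.1 defines hepatic outcomes ("Clinical events that constitute the clinical outcomes endpoint include" progression to F4, decompensation, transplantation or qualification for it, and death). SAP 7.6.3.4 analyses these as event-free survival in the FAS, also without the markers.

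The entry criteria bear on the scores. Protocol 4.3 excludes cirrhosis on biopsy and "Any prior history of decompensated liver disease including ascites, hepatic encephalopathy (HE), or variceal bleeding". Protocol 4.2 limits INR to at most "1.3, unless due to therapeutic anticoagulation", and total bilirubin to the ULN, with an exception for alternate causes such as Gilbert's syndrome or hemolytic anemia. SAP 7.6.3.9 defines the score: "CP score will be calculated as below, ranging from 5-15".

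**The concern.** The aim and the method do not match. A subject's fibrosis stage at Week 24 or Week 96 is partly the stage that the subject entered with. A marker that reflects baseline severity will therefore correlate with later stage even if it says nothing about who improves or worsens. A reader who takes the heading at its word would read that coefficient as prediction.

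On the complications side, the population is non-cirrhotic by design and Child-Pugh has little room to vary at entry. Much of the variation that the exceptions do allow (a raised INR from anticoagulation, a raised bilirubin from Gilbert's syndrome or hemolysis) is not a complication of cirrhosis.

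What is at stake is the marker work itself. Protocol 1.6 says that the study includes these markers to further the development of non-invasive tools, because biopsy has limitations. The primary and secondary efficacy conclusions are not affected.

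**Working it through.** **1. Child-Pugh at entry.** The plan's own range reproduces: five components at 1 to 3 points give 5 × 1 = 5 to 5 × 3 = 15. Setting Protocol 4.2 and 4.3 against the table in SAP 7.6.3.9:

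| Component | Entry limit | 1-point band | Points at entry |
|---|---|---|---|
| INR | ≤ 1.3 (anticoagulation excepted) | < 1.7 | 1 |
| Total bilirubin | ≤ ULN (alternate causes excepted) | < 2 mg/dL | 1, assuming ULN < 2 mg/dL |
| Ascites | any prior history excluded | none | 1 |
| Encephalopathy | any prior history excluded | none | 1 |
| Albumin | no limit stated | > 3.5 g/dL | 1 to 3 |

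Apart from the exceptions, baseline Child-Pugh is 4 + 1 = 5 if albumin is above 3.5 g/dL, and at most 4 + 3 = 7.

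**2. What little variation costs.** The documents do not say how many subjects will exceed 5, so this is a range of assumptions. If a proportion p exceeds 5, a correlation ρ with an underlying continuous severity shrinks to ρ × φ(z_p) / √(p(1−p)). With ρ = 0.5 and n = 120 (Protocol 5.2.2: 3 × 40, an upper bound for the LBAS):

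| p | Expected subjects above 5 | Factor | Observed r | Approximate power, two-sided 5% |
|---|---|---|---|---|
| 1% | 1.2 | 0.268 | 0.13 | 31% |
| 2% | 2.4 | 0.346 | 0.17 | 47% |
| 5% | 6 | 0.473 | 0.24 | 74% |
| 10% | 12 | 0.585 | 0.29 | 90% |

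The power figures are rough where so few subjects exceed 5. If nobody does, the coefficient is undefined.

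**3. Stage against change in stage.** Assumptions: baseline stage is F2 or F3 in equal shares (variance 0.25); change in stage is independent of baseline stage and of the marker, so true prediction is zero; and a baseline marker correlates 0.50 with baseline stage. Then:

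- r(marker, later stage) = 0.50 × √(0.25 / (0.25 + V)), where V is the variance of change.
- r(marker, change) = 0 by construction.
- r(later stage, change) = √(V / (0.25 + V)).

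Scenario A: changes of −2, −1, 0, +1 with probabilities 0.05, 0.35, 0.45, 0.15. The mean is −0.30 and V = 0.70 − 0.09 = 0.61. So r(marker, later stage) = 0.50 × √(0.25/0.86) = 0.27, and r(later stage, change) = √(0.61/0.86) = 0.84.

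Scenario B: probabilities 0.03, 0.20, 0.57, 0.20. The mean is −0.06 and V = 0.52 − 0.0036 = 0.516. The results are 0.29 and 0.82.

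The smallest correlation reaching two-sided p < 0.05 is tanh(1.96/√(n−3)): 0.179 at n = 120, and 0.214 at n = 84 (70% of 120, assumed). A stage correlation of 0.27 would be nominally significant in about 85% of trials at n = 120 and 70% at n = 84, with no prediction of change at all.

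**4. Treatment.** SAP 7.6.3.8 does not say whether arms are pooled. Protocol 1.4.1.3 reports that EFX lowered ELF and Pro-C3. To see why this needs stating, marker and response were simulated as independent within arm, with 40 placebo and 80 EFX subjects. The assumptions were a marker shift of 1.0 to 1.5 SD, one-stage response of 10–20% against 50%, 0 or 15% of non-responders worsening, and 0 or 20% of responders improving by two stages. If the arms were pooled, the mean absolute correlation with on-study stage would be 0.09 to 0.16, and p < 0.05 would occur in about 15% to 43% of trials against a nominal 5%.

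**The case against.** Several points on the other side stand.

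- **Fibrosis stage is not at a floor.** F2–F3 is mid-scale, and on-study stage can run from F0 to F4. Step 3 shows that on-study stage carries much of the information on change (0.82–0.84). A reader might infer that 7.6.3.8 cannot answer its question at all; for fibrosis the documents do not support that.
- **MELD is not shown to be at its minimum.** The documents give no MELD formula and no entry limit on the score. Under the classic formula, taken here as an assumption (3.78 ln bilirubin + 11.2 ln INR + 9.57 ln creatinine + 6.43, inputs floored at 1), MELD is 6.4 at the floor. With bilirubin 1.2 and INR 1.3 it is 10.1 at creatinine 1.0, 12.6 at 1.3 and 14.6 at 1.6. The floor argument rests on Child-Pugh alone.
- **The limits apply only at entry, and albumin has none.** Scores can rise later. However, Protocol 6.25.1 takes subjects out of the study after a hepatic event, and the LBAS needs a biopsy at the relevant time point, so high scores are also curtailed on study.
- **Pooling is not established.** SAP 7.6 says that efficacy analyses are done by treatment group, which may well cover 7.6.3.8. The figures in step 4 show what pooling would do, not what the plan will do.
- **Removing MELD would go too far.** Protocol 6.25.1 itself treats a repeated MELD of 15 or more as an event.
- **The analysis is exploratory and partly out of sight.** The exploratory objectives and endpoints are redacted, Protocol 7.10 allows further analyses in a Biomarker Analysis Plan, and Table 3 speaks of association, which a correlation does address.

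These points limit the concern but do not remove it. The unredacted text of 7.6.3.8 still names stage and scores for an aim worded as prediction of change and complications.

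**Conclusion.** The point holds as a minor improvement. As written, SAP 7.6.3.8 does not specify a test of prediction, and a stage correlation of about 0.27 to 0.29 can arise with none. That figure rests on an assumed 0.50 correlation at baseline, equal F2/F3 shares and the two assumed change distributions. Child-Pugh is a poor stand-in for complications: four of its five components score 1 point at entry, apart from the exceptions for anticoagulation, Gilbert's syndrome and hemolytic anemia, and assuming a bilirubin ULN below 2 mg/dL. That baseline scores will cluster at 5 is an inference, because albumin is unrestricted. The documents do not establish that MELD is at its minimum, that the fibrosis half is uninformative, or that arms will be pooled.

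**What to change.** In SAP 7.6.3.8:

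(a) Relate the baseline value of ELF, Pro-C3 and liver stiffness, and their change from baseline, to change in fibrosis stage (improvement of at least one stage, worsening of at least one stage) at Weeks 24 and 96. State that this is done within arm or adjusted for treatment, in line with the by-treatment rule in SAP 7.6.

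(b) Add a summary of the markers against the Protocol 6.25.1 events already collected (progression to F4 and adjudicated liver events) in the FAS, descriptive if events are few. Keep MELD and Child-Pugh as descriptive only.

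The cost is SAP wording and a few more exploratory tables from data already collected. Part (b) will probably rest on few events.

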7.6.3.9 Change from baseline in markers of liver injury and function

The analysis of markers of liver injury and function, including ALT, AST, ALP, GGT, bilirubin, INR, albumin, uric acid, platelets, MELD score, and CP score will be performed using the FAS and LBAS. Summaries of actual values and changes from baseline will be presented by treatment group and visit.

CP score will be calculated as below, ranging from 5-15:

	1 point	2 point	3 point
Bilirubin (Total)	<2 mg/dL (<34.2 µmol/L)	2-3 mg/dL (34.2-51.3 µmol/L)	>3 mg/dL (>51.3 µmol/L)
Albumin	>3.5 g/dL (>35 g/L)	2.8-3.5 g/dL (28-35 g/L)	<2.8 g/dL (<28 g/L)
INR	<1.7	1.7-2.2	>2.2

CONFIDENTIAL

Statistical Analysis Plan

Sponsor Name: Akero Therapeutics, Inc.
Sponsor Protocol ID: AK-US-001-0102

Ascites	No ascites	Mild to moderate (diuretic responsive/controlled)	Severe (diuretic refractory/poorly controlled)
Encephalopathy	No Encephalopathy	Grade 1-2	Grade 3-4
Class A = 5-6 points			
Class B = 7-9 points			
Class C = 10-15 points			

An MMRM model with baseline covariate will be used to evaluate the changes and percent changes from baseline in markers of liver injury and function between the EFX arms and the placebo arm at scheduled visits, controlling for stratification factors. LS means, 95% CIs, and p-values will be presented.

Summaries and boxplots will be presented for actual values and changes from baseline in ALT, AST, ALP, GGT, bilirubin, INR, albumin, uric acid, MELD score, and CP score at the collection time points defined in the Schedule of Assessments by treatment group.

7.6.3.10 *MRI-PDFF based quantitation of hepatic fat*

The analysis of MRI-PDFF based quantitation of hepatic fat will be performed using the MRI-PDFF Analysis Set. Summaries of actual values and absolute and percent changes from baseline will be presented by treatment group and visit. A CMH test will be used to compare the differences in proportions of subjects with relative reduction $\geq 30\%$ and $\geq 50\%$ in hepatic fat and with liver fat content $\leq 5\%$ at Week 24 and Week 96 between the EFX arms and the placebo arm, adjusting for stratification factors. The point estimates and 95% CIs for the differences in proportions, and p-values will be calculated. The 95% CI will be constructed using the Miettinen and Nurminen method.

7.6.3.11 *Change from baseline in waist-to-hip ratio*

The analysis of change from baseline in waist-to-hip ratio will be performed using the FAS and PPS. Summaries of actual values and changes from baseline will be presented by treatment group and visit. An MMRM model with baseline covariate will be used to evaluate the changes from baseline in waist-to-hip ratio between the EFX arms and the placebo arm at scheduled visits, controlling for stratification factors. LS means, 95% CIs, and p-values will be presented.

7.6.3.12 *Changes from baseline in health-related quality of life (CLDQ-NASH)*

The analysis of changes from baseline in CLDQ-NASH will be performed using the FAS and PPS. Summaries of CLDQ-NASH total score and domain scores will be presented by treatment group and visit. An MMRM model with baseline covariate

CONFIDENTIAL

Statistical Analysis Plan

Sponsor Name: Akero Therapeutics, Inc.
Sponsor Protocol ID: AK-US-001-0102

will be used to evaluate the changes from baseline in total score between the EFX arms and the placebo arm at scheduled visits, controlling for stratification factors. LS means, 95% CIs, and p-values will be presented.

